8.2.5. Pharmacokinetic and Anti-Drug Antibody Procedures

8.2.5.1. Drug Concentration Measurements and Samples

Samples for assessment of evinacumab and alirocumab concentration will be collected at time points listed in [Table 3](#) and [Table 4](#). They will be collected predose and at the end of the IV infusion on days when study drug is administered.

[REDACTED]

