10.4.5. Analysis of Drug Concentration and Target Concentration Data

Descriptive statistics of evinacumab concentrations and total ANGPTL3 concentration and alirocumab and PCSK9 concentration at each sampling time will be provided by treatment group. Plots of mean concentrations (linear and log scales) versus time will be presented.

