5.10. Analysis of Pharmacokinetic Variables

Descriptive statistics of concentrations of total evinacumab, total ANGPTL3, total alirocumab and total PCSK9 will be presented. Mean concentrations of each analyte will be tabulated by visit and treatment group, with concentrations below the LLOQ set to zero.

Plots of the mean concentrations (linear and log scales) will be presented by nominal sampling time. Plots of the individual concentrations (linear and log scales) will be presented by actual sampling time. In the linear-scaled plots, concentrations below the LLOQ will be set to zero; in the log-scaled plots, concentrations below the LLOQ will be imputed as LLOQ/2.

Descriptive statistics will be provided for concentrations of statins at each sampling time. The ratio of concentration at week 24 over baseline will be presented for individual patient, when available.

Descriptive comparison of concentrations of evinacumab and total ANGPTL3 between Caucasian patients and Japanese patients may be performed, if sufficient data are collected.

When appropriate, relationship between concentrations of evinacumab and LDL-C or other biomarkers may be evaluated descriptively.

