6.4. Visit Windows

Visit windows will be programmatically imposed on those efficacy and safety measures repeatedly collected over the course of the study. These visit windows are derived from the number of days in study, specifically assigning day ranges to represent the study assessment schedule provided in the protocol. Data analyzed by time point (including efficacy, laboratory safety data, vital signs, ECG, quality of life, drug concentration and ADA) will be summarized using the analysis windows given in Appendix 10.2 (i.e. efficacy analysis windows for efficacy and global analysis windows for safety). These analysis windows will be applicable for all analyses, and they are defined to provide more homogeneous data for time point-specific analyses. If multiple valid values of a variable exist within an analysis window, the nearest from the targeted study day will be selected for analysis, unless otherwise specified. If the difference is a tie, the value after the targeted study day will be used. If multiple valid values of a variable

exist within a same day, then the first value of the day will be selected when time is available, else the scheduled visit will be selected.

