10.2. Windows for Analysis Time Points

Below are the definitions for the visit windows programmatically imposed on measures repeatedly collected over the course of the study. These visit windows reflect the study schedule of assessments as described in the protocol.

The visit windows are constructed using ranges applied to the number of days in study (study days) when the measure is collected. Below are the relevant definitions for the analysis visit windows:

1. Study day is defined as the number of days since the first study treatment administration +1. The first study treatment occurs on
2. Study Day 1.
3. Open-label study day is defined as the number of days since the first open-label study treatment administration+1
4. Since the protocol specifies that measurements be collected before study treatment is administered on a given day, it is appropriate that baseline include Day 1.
5. For randomized but not treated patients, Day 1 is the day of randomization.

Table 1: Global Analysis Windows

Visit label	Targeted Study Day	Targeted Open-Label Study Day	Analysis Window in Study Day
Screening	< Day 1	N/A	Measurement obtained prior to first study treatment, and not defined as baseline visit
Baseline	1	N/A	Measurement obtained closest to first study treatment, while remaining prior to first study treatment
Week 2	15	N/A	2 to 21
Week 4	29	N/A	22 to 42
Week 8	57	N/A	43 to 70
Week 12	85	N/A	71 to 98
Week 16	113	N/A	99 to 126
Week 20	141	N/A	127 to 154
Week 24	169	Day 1	155 to 182 for patients not entering OLTP or 155 to first OL treatment day for patients entering OLTP
Week 28	197	29	first OL treatment day+1 to 210
Week 32	225	57	211 to 238
Week 36	253	85	239 to 266
Week 40	281	113	267 to 294
Week 44	309	141	295 to 322
Week 48	337	169	323 to 350
FU – W4	For patients prematurely discontinued trt: last study trt to 28 days after last study trt For patients completed OLTP: 365	For patients prematurely discontinued trt: last study trt to 28 days after last study trt For patients completed OLTP: 197	For patients prematurely discontinued trt: Last study trt day +1 to 56 days after last study trt For patients completed OLTP: 351 to 392

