2. Study assessments will be performed and blood samples will be collected before the dose of study drug in all patients. For patients undergoing apheresis: Study assessments will be performed and blood samples will be collected immediately before the lipid-apheresis procedure; study drug will be administered after the apheresis procedure. The timing between the baseline sample collection relative to the most recently completed LDL apheresis procedure, administration of a PCSK9 inhibitor or mipomersen should match the timing of the week 24 sample collection relative to the most recently completed LDL apheresis procedure, administration of a PCSK9 inhibitor or mipomersen. Depending on the duration between the LDL apheresis procedure and sample collection, the visit window may not apply.
3. Fasting sample will be collected for the lipid panel: total-C, calculated LDL-C, HDL-C, TG, non-HDL-C
4. Fasting sample will be collected for specialty lipid panel: Apo B, Apo A-1, and Lp(a)
5. On dosing days, vital signs should be recorded prior to IV infusion, and 30 minutes and 60 minutes post-IV infusion
6. ECG should be performed before blood samples are collected at visits requiring blood draws.
7. Assessment of Tanner Stage and sex hormones (includes luteinizing hormone, follicle stimulating hormone, estradiol, total testosterone) only applicable to patients <18 years old.
8. All laboratory samples should be collected before administration of study drug.
9. WOCBP only, confirm required contraception use and reminder pregnancy reporting
10. The ADA sample should be drawn before study drug administration
11. For patients who are not undergoing apheresis, the PK sample should be drawn before the dose of study drug and at the end of the infusion. For patients undergoing apheresis, a PK sample should be collected immediately before the apheresis procedure and a PK sample should be collected immediately after the apheresis procedure, prior to administration of study drug, and, again at the end of the infusion of study drug.
12. Including assay of total ANGPTL3.
13. Should be collected at the baseline visit, or at any study visit
14. All end of treatment (EOT) assessments will be performed and blood samples will be collected before the dose of open-label study drug in all patients. For patients undergoing

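### Read literally, SAP 5.10 and 6.4 leave every end-of-infusion and post-apheresis value out of the concentration table that the protocol promised by sampling time

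*SAP*

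**What the plan says.** **Sampling.** Protocol 8.2.5.1 says of the evinacumab and alirocumab samples: "They will be collected predose and at the end of the IV infusion on days when study drug is administered". Footnote 11 to the treatment-period schedule in SAP 10.9 says that, without apheresis, "the PK sample should be drawn before the dose of study drug and at the end of the infusion". With apheresis there is a sample before the procedure, and then "a PK sample should be collected immediately after the apheresis procedure, prior to administration of study drug, and, again at the end of the infusion". Total ANGPTL3 and PCSK9 are measured in the same samples (Protocol 8.2.6).

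**Reporting.** Protocol 10.4.5 says that descriptive statistics for evinacumab, ANGPTL3, alirocumab and PCSK9 "at each sampling time will be provided by treatment group". SAP 5.10 says instead: "Mean concentrations of each analyte will be tabulated by visit and treatment group". For the figures the same section says "Plots of the mean concentrations (linear and log scales) will be presented by nominal sampling time", and it plots individual values by actual sampling time. It also summarises statin concentrations at each sampling time.

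**Selection of values.** SAP 6.4 lists drug concentration among the data placed in the Appendix 10.2 windows and says that the windows apply to all analyses. For several values on one day, "the first value of the day will be selected when time is available". In Table 1 of SAP 10.2, Baseline must precede the first treatment, Week 2 starts on day 2, and Week 24 runs "155 to first OL treatment day for patients entering OLTP".

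**Declared changes.** SAP 1.2.4 lists one departure from the protocol's statistical section. It concerns the safety analysis set, not PK reporting.

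**The concern.** The protocol's reporting unit is the sampling time and the SAP table's unit is the visit. At a dosing visit with PK sampling these differ, because one visit holds a trough, an end-of-infusion value and, in some patients, a post-apheresis value. A general rule that picks one value per day suits lipids and safety laboratory tests, where a second same-day value is a repeat. It does not suit PK, where the same-day values are different planned measurements.

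Determining evinacumab concentrations in these patients is a secondary objective (Protocol 2.2, SAP 1.2.2). At stake is whether the study report contains a numerical summary of end-of-infusion and post-apheresis concentrations, or only pictures of them. The same holds for the target concentrations.

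**Working it through.** The plan states no figure to reproduce here. The check is a count of scheduled samples to week 48 from the SAP 10.9 schedule, set against what the SAP 6.4 rule keeps.

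1. **PK visits:** weeks 0, 2, 4, 8, 12, 16, 20, 24, 36 and 48, which is 10 visits.
2. **Dosing visits:** weeks 0, 4, 8, 12, 16 and 20 (double-blind) and 24, 28, 32, 36, 40 and 44 (open-label), which is 12 visits.
3. **Both:** weeks 0, 4, 8, 12, 16, 20, 24 and 36, which is 8 visits. Dosing weeks 28, 32, 40 and 44 have no PK sample. PK weeks 2 and 48 have no dosing.
4. **Scheduled samples without apheresis:** 8 × 2 + 2 × 1 = 18.
5. **Scheduled samples with apheresis, assuming a procedure at all eight dosing PK visits:** 8 × 3 + 2 × 1 = 26 if weeks 2 and 48 give one sample each, or 8 × 3 + 2 × 2 = 28 if they give two.
6. **Kept by one value per visit:** 10 in every case.
7. **Omitted from the table:**
   - without apheresis, 18 − 10 = 8, and 8/18 = 44%;
   - with apheresis, 26 − 10 = 16, and 16/26 = 62%, or 28 − 10 = 18, and 18/28 = 64%.

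The first sample of a dosing day is the pre-dose one, or the pre-apheresis one. The omitted values are therefore all the end-of-infusion and all the post-apheresis samples, not a random subset.

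Two samples have a further problem with the windows:

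- **Day 1, end of infusion.** Baseline admits only values before the first treatment, and Week 2 starts on day 2. This sample has no window under any same-day rule. Appendix 10.2 lets Baseline include day 1 on the premise that measurements precede dosing, and this sample is the exception.
- **Week 24, end of infusion.** This sample follows the first open-label evinacumab infusion. The Week 24 window includes that day and Week 28 starts the day after, so the sample carries the Week 24 label. Under SAP 6.4 it is then passed over for the pre-dose value, and the first open-label end-of-infusion value has no row.

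**The case against.** The strongest reply is that 5.10 can be read as a table with nominal-time rows inside each visit. The mean plots by nominal sampling time require those means to be computed anyway, SAP 4.10 defines the PK variables at each time point, and 5.10 does not expressly withdraw the protocol's promise. The table shells, which might settle it, are not in the documents. This is a possible reading, but not the stated one. The section uses sampling time for the statins and the plots and visit for this table, and 6.4 explicitly covers drug concentration. The generous reading also leaves the day-1 end-of-infusion sample without a window.

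Several other replies stand and limit the point:

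- The values are not lost to the report, because the mean and individual plots show them.
- The value kept is the trough. The dose rationale (Protocol 3.2.2) concerns concentrations above 100 mg/L for about four weeks, and a trough table under four-weekly dosing speaks to that directly.
- The apheresis counts are maxima, since they assume a procedure at every dosing PK visit.
- PK reporting is descriptive.

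A reader might infer that the table will average trough with end-of-infusion values, or that evinacumab will show up in the placebo group's Week 24 mean. The documents do not support this. Nothing in the SAP tells the analyst to average several samples from one patient at a visit. SAP 6.4 selects one, and at week 24 the one selected precedes the open-label dose. Table 1 also marks that row as open-label day 1, and SAP 3.4 confines the placebo and evinacumab labels to the double-blind period.

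A reader might also infer that a comparison of concentrations after and before apheresis is owed. No stated objective or endpoint asks for it, so it would be an added analysis rather than a repair.

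**Conclusion.** The point holds as a minor one. The SAP replaces the protocol's table by sampling time with a table by visit, does not declare the change, and applies a same-day rule that leaves out 8 of 18 scheduled samples per patient without apheresis and up to 16 of 26 or 18 of 28 per patient with it. One further sample, at the end of the first infusion, has no window at all. The first open-label end-of-infusion sample sits under a label that does not identify it.

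The size rests on three assumptions: 6.4 is applied literally to the 5.10 table, sampling times are recorded, and, for the apheresis figures, a procedure takes place at all eight dosing PK visits. The effect is confined to descriptive tables of drug and target concentrations. No primary or key secondary test is touched.

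**What to change.** - **SAP 5.10:** tabulate by visit and nominal sampling time within the visit, with rows for pre-dose (pre-apheresis where applicable), post-apheresis before dosing, and end of infusion.
- **SAP 6.4:** exempt PK and target concentrations from the same-day selection.
- **SAP 10.2:** give the day-1 end-of-infusion sample its own row, and report the week-24 end-of-infusion sample under the first open-label dose.

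This restores what Protocol 10.4.5 promises, so no entry in SAP 1.2.4 is then needed. If the sponsor prefers a trough-only table, 5.10 should say so and 1.2.4 should list it. The cost is SAP wording and table shells. The samples are already scheduled, and the plots already need their sampling times.

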Randomization	X ¹													
Administer IV Double-Blind Study Drug	X ¹		X	X	X	X	X							
Administer IV Open-Label Study Drug								X ¹⁰	X	X	X	X	X	
Concomitant Medications (including LMT and apheresis)	X	X	X	X	X	X	X	X	X	X	X	X	X	X
Query LMT compliance	X ¹	X	X	X	X	X	X	X	X	X	X	X	X	X
Efficacy:														
Lipid Panel ^{2,3}	X	X	X	X	X	X	X	X	X	X	X	X	X	X
Specialty Lipid Panel ^{2,4}	X		X	X	X	X		X		X		X		X
Safety:														
Adverse Events	X	X	X	X	X	X	X	X	X	X	X	X	X	X
Physical Examination								X				X		X
Measured Height														
Body Weight	X		X	X	X	X	X	X	X	X	X	X	X	X
Vital Signs (pulse rate, BP) ⁵	X	X	X	X	X	X	X	X	X	X	X	X	X	X
Electrocardiogram ⁶								X						X
Confirm contraception use and reminder of pregnancy reporting	X ¹		X	X	X	X	X	X	X	X	X	X	X	X
Remind male patients to use condoms	X		X	X	X	X	X	X	X	X	X	X	X	X
Laboratory Testing⁷ :														
Hematology	X		X	X	X	X		X		X		X		X

Study Procedure	Double-Blind Treatment Period								Open-Label Treatment Period					
	2	3	4	5	6	7	8	9 End DBTP ¹ 3	10	11	12	13	14	15 End of OLTP
Day	1	15	29	57	85	113	141	169	197	225	253	281	309	337
Visit Window (Day)	±1	±3	±3	±3	±3	±5	±5	±1	±5	±5	±5	±5	±5	±5
Week	0	2	4	8	12	16	20	24	28	32	36	40	44	48
Blood Chemistry	X		X	X	X	X		X		X		X		X
Creatine Phosphokinase	X		X	X	X	X		X		X		X		X
Serum Pregnancy Test ⁸														X
Urine Pregnancy Test ⁸	X		X	X	X	X	X	X	X	X	X	X	X	
Urinalysis	X		X	X	X	X		X		X		X		X
hs-CRP	X							X						X
HbA1C	X ¹				X			X			X			X
LDLR function	X ¹													
Research Samples	X ¹		X	X		X		X	X					
PK and PD Samples														
ADA Sample ⁹	X ¹		X		X			X						X
PK (evinacumab, alirocumab), ANGPTL3, PCSK9 samples ^{10,11}	X ¹	X	X	X	X	X	X	X			X			X
PK of statin ¹⁰	X ¹					X								
DNA sample for HoFH genotyping	X ¹													
XXXXXXXXXX	X ¹													
Other:														
EQ-5D	X							X						
HADS	X ¹							X				X ¹⁴		X ¹⁴
Review of diet	X ¹	X	X	X	X	X	X	X	X	X	X	X	X	X

Table 4: Schedule of Events – Follow-up Period

Study Procedure	Follow-up Period ⁵				
	16 ⁴	PV17 ^{4,5}	18 ⁴	PV19 ^{4,5}	EOS 20
Visit	365	393	421	449	477
Day	±5	±5	±5	±5	±5
Week	52	56	60	64	68
Treatment:					
Concomitant Medications (including LMT and apheresis)	X	X	X	X	X
Query LMT compliance	X	X	X	X	X
Safety:					
Adverse Events	X	X	X	X	X
Physical Examination					X
Measured Height					
Body Weight					X
Vital Signs (pulse rate, BP)					X
Electrocardiogram ¹					X
Confirm contraception use and reminder of pregnancy reporting	X	X	X	X	X
Remind male patients to use condoms	X	X	X	X	

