8.2.5.3. Statin Concentrations

Samples for statin concentration will be collected at time points shown in [Table 3](#).

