10.4.7. Analysis of Statin Concentration

Descriptive statistics at each sampling time. The ratio of concentration at week 24 over baseline for individual patient will be presented, when available.

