Pharmacogenomics Consent	X ¹													
Treatment:														
Randomization	X ¹													
Administer IV Double-Blind Study Drug	X ¹		X	X	X	X	X							
Administer IV Open-Label Study Drug								X ¹⁰	X	X	X	X	X	
Concomitant Medications (including LMT and apheresis)	X	X	X	X	X	X	X	X	X	X	X	X	X	X
Query LMT Compliance	X ¹	X	X	X	X	X	X	X	X	X	X	X	X	X
Efficacy:														
Lipid Panel ^{2,3}	X	X	X	X	X	X	X	X	X	X	X	X	X	X
Specialty Lipid Panel ^{2,4}	X		X	X	X	X		X		X		X		X
Safety:														
Adverse Events	X	X	X	X	X	X	X	X	X	X	X	X	X	X
Physical Examination								X				X		X
Measured Height														X
Body Weight	X		X	X	X	X	X	X	X	X	X	X	X	X
Vital Signs (pulse rate, BP) ⁵	X	X	X	X	X	X	X	X	X	X	X	X	X	X
Electrocardiogram ⁶								X						X
Tanner stage ⁷								X						X
Confirm contraception use and reminder of pregnancy reporting	X ¹		X	X	X	X	X	X	X	X	X	X	X	X
Remind male patients to use condoms	X		X	X	X	X	X	X	X	X	X	X	X	X
Laboratory Testing⁸:														
Hematology	X		X	X	X	X		X		X		X		X

Study Procedure	Double-Blind Treatment Period								Open-Label Treatment Period					
	2	3	4	5	6	7	8	9 End DBTP ¹⁴	10	11	12	13	14	15 End of OLTP
Day	1	15	29	57	85	113	141	169	197	225	253	281	309	337
Visit Window (Day)	±1	±3	±3	±3	±3	±5	±5	±1	±5	±5	±5	±5	±5	±5
Week	0	2	4	8	12	16	20	24	28	32	36	40	44	48
Blood Chemistry	X		X	X	X	X		X		X		X		X
Creatine Phosphokinase	X		X	X	X	X		X		X		X		X
Serum Pregnancy Test ⁹														X
Urine Pregnancy Test ⁹	X		X	X	X	X	X	X	X	X	X	X	X	
Sex Hormones ⁷								X						X
Urinalysis	X		X	X	X	X		X		X		X		X
hs-CRP	X							X						X
HbA1C	X ¹				X			X			X			X
LDLR function	X ¹													
Research Samples	X ¹		X	X		X		X	X					
PK and PD Samples														
ADA Sample ¹⁰	X ¹		X		X			X						X
PK (evinacumab, alirocumab), ANGPTL3, PCSK9 Samples ^{11,12}	X ¹	X	X	X	X	X	X	X			X			X
PK of statin ¹¹	X ¹					X								
DNA sample for HoFH genotyping	X ¹													
██████████ ██████████	X ¹													
Other:														
EQ-5D	X							X						
HADS	X ¹							X				X ¹⁵		X ¹⁵
Review of diet	X ¹	X	X	X	X	X	X	X	X	X	X	X	X	X

Table 4: Schedule of Events – Follow-up Period

Study Procedure	Follow-up Period ⁵				
	16 ⁵	PV17 ^{5,6}	18 ⁵	PV19 ^{5,6}	EOS 20
Day	365	393	421	449	477
Visit Window (Day)	±5	±5	±5	±5	±5
Week	52	56	60	64	68
Treatment:					
Concomitant Medications (including LMT and apheresis)	X	X	X	X	X
Query LMT Compliance	X	X	X	X	X
Safety:					
Adverse Events	X	X	X	X	X
Physical Examination					X
Measured Height					
Body Weight					X

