6.5. Unscheduled Assessments

For efficacy, safety laboratory data, vital signs, ECG, ED-5D, and HADS, unscheduled visit measurements may be used to provide a measurement for a time point, including baseline, if appropriate according to their definitions. The measurements may also be used to determine abnormal values, AESIs, and PCSVs.

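### The per-patient statin ratio is defined at week 24, but statin samples are scheduled only at baseline and week 16

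*SAP*

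**What the plan says.** Two statin outputs are planned. The first is a summary by visit: "Descriptive statistics will be provided for concentrations of statins at each sampling time" (SAP 5.10). The second is a per-patient ratio: "The ratio of concentration at week 24 over baseline will be presented for individual patient, when available" (SAP 5.10). Protocol 10.4.7 has almost the same sentence, "The ratio of concentration at week 24 over baseline for individual patient will be presented, when available", both in the version for patients aged 18 and over and in the version for patients aged 12 and over.

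The sampling times come from one place. Protocol 8.2.5.3 says "Samples for statin concentration will be collected at time points shown in" Table 3, and gives no times of its own. In Table 3 the row is labelled "PK of statin ¹⁰" in the adult version and "PK of statin ¹¹" in the version from age 12. SAP 10.9 reproduces the row. The follow-up schedules contain no statin row.

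SAP 4.10 names the statins measured: rosuvastatin, atorvastatin and simvastatin.

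**The concern.** The ratio needs two concentrations from the same patient, and the schedule provides for only one of the two named. A qualifier about availability covers a patient who misses a draw. It does not supply a draw that no patient is due to have.

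What is at stake is modest but real. The risk/benefit section (Protocol 3.2.3) argues from mechanism that evinacumab should not affect the enzymes and transporters that govern statin disposition. The statin samples are the trial's own data on that expectation. Patients enter on individual, maximally tolerated regimens and three different statins are measured, so pooled concentrations at a visit mix drugs and doses. Background therapy is meant to stay stable, so a within-patient ratio removes most of that variation. It is the only planned statin output that does so, and as defined it would come out empty while the week 16 samples went unused for it.

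**Working it through.** No power or error-rate figure bears on this point. The check is a reading of the schedule, followed by a test of whether any other rule could supply a week 24 value.

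**1. Columns of the schedule.** The main table has 14 visit columns, at weeks 0, 2, 4, 8, 12, 16, 20, 24, 28, 32, 36, 40, 44 and 48. Reading off the marked cells:

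| Row | Cells | Weeks marked |
|---|---|---|
| Statin PK, Protocol Table 3 (18 and over) | 14 | 0, 16 |
| Statin PK, Protocol Table 3 (12 and over) | 14 | 0, 16 |
| Statin PK, SAP 10.9 | 14 | 0, 16 |
| HbA1c (control) | 14 | 0, 12, 24, 36, 48 |
| ADA (control) | 14 | 0, 4, 12, 24, 48 |
| hs-CRP (control) | 14 | 0, 24, 48 |
| EQ-5D (control) | 14 | 0, 24 |
| Evinacumab/alirocumab PK (control) | 14 | 0, 2, 4, 8, 12, 16, 20, 24, 36, 48 |

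The control rows give the expected visits and the three statin rows agree, so a shifted column in the extracted text is unlikely.

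**2. Analysis windows.** SAP 6.4 applies the windows to "Data analyzed by time point (including efficacy, laboratory safety data, vital signs, ECG, quality of life, drug concentration and ADA"), so a concentration could in principle be moved to another visit. The week 16 visit is day 113 ± 5, that is days 108 to 118. The SAP 10.2 window for week 16 is days 99 to 126, which contains all of them. The week 24 window opens on day 155:

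- from the latest on-schedule week 16 visit: 155 − 118 = 37 days;
- from the target day: 155 − 113 = 42 days.

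No on-schedule week 16 sample can be counted as week 24.

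**3. Unscheduled samples.** SAP 6.5 says "unscheduled visit measurements may be used to provide a measurement for a time point, including baseline", but only for efficacy, safety laboratory data, vital signs, ECG and the two questionnaires. Drug concentrations are not in the list.

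**4. Other week 24 blood.** Evinacumab, alirocumab, ANGPTL3 and PCSK9 samples are drawn at week 24. Statin PK is a separate row, and no visible text says statins are assayed from the other tubes.

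**Result.** Scheduled statin samples that could serve as the week 24 numerator: 0. With week 16 as the numerator, both samples are scheduled.

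**The case against.** The mismatch itself is hard to dispute; the case against concerns its weight and the remedy.

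- **It is a small output.** Statin exposure is not a study objective, and the protocol's PK variable is evinacumab concentration. The ratio has no test, interval or decision rule, and the no-interaction argument rests on mechanism. The by-visit summaries still report the baseline and week 16 data. All of this stands, and it keeps the point minor.
- **Never available is too strong.** An off-schedule draw, or a statin assay run on another week 24 sample, could yield a ratio, and some text near the PK procedures is redacted. This stands as a matter of wording: what the documents show is that the sample is never scheduled.
- **The error could be in the schedule.** A missing week 24 mark would explain the mismatch equally well, and the protocol matches sample timing between baseline and week 24, not week 16. The documents do not settle which side was intended. But the matching rule concerns apheresis, PCSK9 inhibitors and mipomersen, not statin intake, and three schedule copies agree on week 16.
- **A pre-dose sample is ambiguous in apheresis patients.** The PK footnote (10 in the adult protocol, 11 in SAP 10.9) asks for a draw before apheresis and another after it, both before study drug. This stands and belongs in the fix.
- **57 is not the right denominator.** Only patients on one of the three measured statins could contribute, and the documents give no count. This stands, but the number with a scheduled numerator is zero under any denominator.

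**Conclusion.** The point holds. SAP 5.10 and both versions of Protocol 10.4.7 define the only within-patient statin output at a visit where no statin sample is scheduled. None of the 57 planned patients has a scheduled numerator. With week 16 in its place, every patient on a measured statin with both draws would contribute; how many that is cannot be stated from the documents.

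The conclusion assumes that the three schedule copies were read correctly from the PDF and that no redacted text adds a week 24 statin assay. The consequence is limited to one descriptive pharmacokinetic output; the efficacy conclusions are unaffected.

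**What to change.** Define the ratio as week 16 over baseline in SAP 5.10 and in Protocol 10.4.7 of both versions, and say which draw is used: the pre-infusion sample, and for apheresis patients either the pre-apheresis or the post-apheresis draw, the same one at both visits. At week 16 the pre-infusion sample follows four infusions (day 1 and weeks 4, 8 and 12), so it still addresses statin exposure under repeated dosing.

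SAP 1.2.4 already lists departures from the protocol's statistical section, and SAP 1 allows revision before the first-step database lock. The change can be entered there as a second item, with the protocol text aligned at the next amendment. The cost is one time point in three places plus a sentence on the draw, with no extra blood or assays.

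If week 24 was really intended, a statin mark must be added at week 24 in Table 3 of both protocol versions and in SAP 10.9. That costs an additional sample and assay for each patient on a measured statin, and is possible only for patients who have not yet passed that visit.
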